### **2.2 Secondary objectives**

Secondary objective of this study is:

-To test the predictive value of cytokine/chemokine changes measured in the 3rd and 6th months on the PASAT, SDMT, 9-Hole peg test, timed 25-foot walk, EDSS and relapse rate observed after 6 months of treatment.

### **3      Investigational plan**

#### **3.1    Study design**

This study is a multi center, open label study.

80 relapsing remitting MS (RRMS) patients will be recruited according to the Mc Donald's criteria and 60 healthy controls will be recruited as the control group. All subjects will sign an informed consent that will be approved by the local Ethics Committee and the applicable health authorities prior to venipuncture. Basal EDSS, relapses during the last 2 years, paced auditory serial addition task (PASAT), 9-Hole peg test, timed 25-foot walk and single digit modalities test (SDMT) scores will be recorded before study entry. Serum and blood samples will be collected from each participant after evaluation for inclusion and exclusion criteria. Additional serum and blood samples at 2 different time points will be collected from MS patients at months 3 ( $\pm 1$  week) and 6 ( $\pm 2$  weeks) after starting fingolimod 0.5 mg/day po. treatment (Figure 1). Serum samples will be stored at -20°C at local centers for a longest duration of two weeks and kept frozen at -80°C

[figure not shown]
until assayed. The levels of IL-4, IL-6, IL-8, IL-9, IL-10, IL-13, IL-17, IL-23, IFN- $\gamma$ , TNF- $\alpha$ , VLA4, CCL2, CCL5, CXCR3, CXCL13 will be measured by ELISA according to the manufacturer's protocols. Optical density (OD) will be measured at 450 nm and cytokine/chemokine concentrations (pg/ml) will be calculated by referring to a standard curve.

Whole blood samples will be dispatched

In order to perform flow cytometry assay for intracellular cytokine measurement PBMC will be isolated freshly.

EDSS and relapses will be recorded after 6 months of treatment. PASAT, 9-hole peg test, timed 25-foot walk and SDMT's will be performed only at study entry and termination after 6 months (Figure 1).

**Figure 1:** Study protocol (PASAT: Paced auditory serial addition task, SDMT: single digit modalities test, FACS: Flow assisted cell sorting, flow cytometry)

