### **3.6 Risks and benefits**

The risk to subjects in this trial will be minimized by compliance with the inclusion/exclusion criteria, close clinical monitoring, and minimal study duration which will be planned as 1,5 years enrollment time and 6 months follow up.

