### **5.4 Treating the patient**

#### **5.4.1 Patient numbering**

Each patient is uniquely identified by a Subject Number which is composed by the site number assigned by Novartis and a sequential number assigned by the investigator. Once assigned to a patient, the Subject Number will not be reused.

Upon signing the informed consent form, the patient is assigned the next sequential number as given by the investigator using the next blank CRF book.

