#### **6.5.1 Laboratory evaluations**

Blood samples will be collected from each patient and healthy control after evaluation for inclusion and exclusion criteria. Additional blood samples at 2 different time points will be collected from MS patients at months 3 ( $\pm 1$  week) and 6 ( $\pm 2$  weeks) after starting fingolimod 0.5 mg/day po. treatment. Serum samples will be sent to the central laboratory (DETAE) for flow cytometry assay on the same day they are collected. Serum samples will be stored at -20°C at local centers for a longest duration of two week and kept frozen at -80°C [REDACTED]

The levels of IL-4, IL-6, IL-8, IL-9, IL-10, IL-13, IL-17, IL-23, IFN- $\gamma$ , TNF- $\alpha$ , VLA4, CCL2, CCL5, CXCR3, CXCL13 will be measured by ELISA according to the manufacturer's protocols. Optical density (OD) will be measured at 450 nm and cytokine/chemokine concentrations (pg/ml) will be calculated by referring to a standard curve.

In order to perform the flow cytometry assay freshly purified peripheral blood mononuclear cells (PBMC) from venous blood will be stimulated for 24 h by a combination of phorbol ester (PMA, 50 ng/ml) and Ca2+ Ionophore (Ionomycin, 250 ng/ml). The combination of these two stimuli will be used to achieve the strongest stimulus for intracytoplasmic cytokine secretion. Monensin will be added at a final concentration of 1 mM. After stimulation, the cells will be washed with PBS and will be stained with anti-CD4, anti-CD8, anti-CD25, and then fixed and permeabilized. After washing with PBS, the cells will be stained with PE-conjugated anti-IL-4, anti-IL-6, anti-IL-9, anti-IL-10, anti-IL-13, anti-IL-17, anti-IFN- $\gamma$ , anti-TNF- $\alpha$  for 30 min at room temperature and analyzed by flow cytometry.

Cytokine and chemokine levels will be analyzed cumulatively at the end of the study. The results will be recorded to the blood sampling logs and laboratory logs cumulatively.

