6.5 ASSESSMENT OF CYTOKINE AND CHEMOKINE LEVELS

6.5.1 ELISA

Subjects' **IL-4, IL-6, IL-8, IL-9, IL-10, IL-13, IL-17, IL-23, IFN- γ , TNF- α , VLA4, CCL2, CCL5, CXCR3 and CXCL13** values will be tabulated by calculating mean and standart error and compared as Control group vs. Visit 1 (MS patients), Visit 1 (MS patients) vs. Visit 2 (MS patients), Visit 1 (MS patients) vs. Visit 3 (MS patients) and Control group vs. Visit 3 (MS patients) by using appropriate statistical test. Mann Whitney U test with significance level of 0.05 was used for the independent variables since non-normal distributions had been observed. Wilcoxon test was used for the dependent variables with non-normal distributions. For the independent variables with normal distributions Independent Sample t test was used whereas Paired sample t test was used for the dependent variables with normal distributions.

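### Controls are not balanced by centre or calendar time and the SAP's control-versus-MS tests have no centre term, so any centre, storage or run difference shared unevenly between the groups adds to the apparent disease difference

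*Protocol*

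**What the plan says.** - **Centres.** Protocol 3.1: "This study is a multi center, open label study". The number of centres is not stated.
- **Serum.** Protocol 3.1 sets one rule for every site: "Serum samples will be stored at -20°C at local centers for a longest duration of two weeks and kept frozen at -80°C". Protocol 6.5.1 adds: "Cytokine and chemokine levels will be analyzed cumulatively at the end of the study". SAP section 6 repeats this.
- **Flow cytometry.** Protocol 6.5.1: "In order to perform the flow cytometry assay freshly purified peripheral blood mononuclear cells (PBMC) from venous blood will be stimulated for 24 h". Samples go to a central laboratory "for flow cytometry assay on the same day they are collected".
- **Calendar span.** Protocol 3.6 plans "1,5 years enrollment time and 6 months follow up".
- **Controls.** The control inclusion criteria (synopsis and 4.1) ask in substance for healthy adults over 18, and Table 6-2 has them sampled once. Neither place mentions centre or recruitment date. The sample-size text (Protocol 9.8, SAP 5.1) speaks of matched pairs but names no matching variable.
- **Analysis.** SAP 6.5.1 has the markers "compared as Control group vs. Visit 1 (MS patients), Visit 1 (MS patients) vs. Visit 2 (MS patients"), followed by Visit 1 against Visit 3 and controls against Visit 3. SAP 6.5.2 does the same for flow cytometry. Between-group tests are Mann-Whitney or independent t; within-patient tests are Wilcoxon or paired t. There is no term for centre, plate, run or storage time.
- **Centre is available for patients.** Protocol 5.4.1 makes the Subject Number "composed by the site number assigned by Novartis and a sequential number assigned by the investigator".

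**The concern.** The primary objective is a comparison of two separately recruited groups. Protocol 3.2 argues that the design is free of bias because patients act as their own controls, but that argument does not reach a comparison with healthy people. A study that followed the plan exactly could take all 60 controls at one centre in one month, while patients came from every centre over 18 months. Group would then be tied to centre, to serum storage age and, for flow cytometry, to run date. The planned tests could not separate an offset from any of these from a difference between healthy people and MS patients. Control allocation and plate layout cannot be repaired once samples are collected and assayed.

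**Working it through.** **Inputs.** IL-17 mean 32 pg/ml, SD 15, design difference 7, power 90%, alpha 0.05, 60 per group (Protocol 9.8, SAP 5.1). Enrolment 18 months, follow-up 6 months (Protocol 3.6). Assumptions of this check: the same SD in controls, a two-sided test, and the size of any offset.

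**1. The plan's own figure.** n = (15 × (1.960 + 1.282) / 7)² = 48.2, so 49 pairs by the normal approximation. With the noncentral t, 50 pairs give 89.9% power. The stated 50 pairs is reproduced if 15 is taken as the SD of the paired differences. The inputs are therefore usable for illustration.

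**2. Timing.** Collection spans 18 + 6 = 24 months. Flow cytometry on fresh cells must follow that span. If serum is assayed together at the end, each Visit 1 sample is about 6 months older than the same patient's Visit 3 sample, and storage age also depends on when a person was enrolled.

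**3. Between-group bias from a centre offset.** Suppose some centres read D pg/ml differently, and the share of subjects from those centres differs by s between patients and controls. The bias is b = D × s. With SE = 15 × √(2/60) = 2.74, the rejection rate when there is no true difference is 1 − Φ(1.96 − b/SE) + Φ(−1.96 − b/SE).

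| Assumed offset D | Assumed share difference s | Bias b (pg/ml) | False-positive rate |
|---|---|---|---|
| any | 0 | 0 | 5.0% |
| 3.2 (10% of 32) | 0.25 | 0.8 | 6.0% |
| 3.2 | 0.50 | 1.6 | 9.0% |
| 6.4 (20% of 32) | 0.25 | 1.6 | 9.0% |
| 6.4 | 0.50 | 3.2 | 21.5% |

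With the t distribution on 118 degrees of freedom, the 1.6 and 3.2 rows become 8.9% and 21.2%. Those biases are 1.6/7 = 23% and 3.2/7 = 46% of the design difference. If 80 patients rather than 60 enter, b = 3.2 gives 23.9%.

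**4. Within-patient contrasts.** A constant centre offset appears in both visits of the same patient and cancels. What does not cancel is storage age (step 2), visits placed on different plates, time at -20°C that differs by visit, and drift of the flow runs. The documents give no figure from which to size any of these.

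**5. What balanced recruitment achieves.** If controls are recruited over the same period as patients, their storage age and run dates match those of Visit 1. They do not match Visit 3, which is collected about 6 months later, so controls against Visit 3 still needs a drift check.

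**The case against.** The strongest reply is that the plan limits the scope for such differences. One storage rule binds all sites, and Protocol 8.3 says laboratory samples are processed centrally, so centres do not measure the markers themselves. A tolerance of 0 to 14 days is not evidence that centres differ, or that patients and controls are handled differently. Both the offset and the imbalance in the table are chosen, and at equal shares the bias is zero. All of this stands, and it is why the error rates are an illustration.

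A reader might go further and infer three things that the documents do not support:

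- *That serum assays are spread over two years.* The text puts cytokine and chemokine analysis at the end of the study, and the sentence that follows in 6.5.1, on laboratory logs, suggests that the assay is meant. Only collection and the flow runs span two years. If the sentence instead means data analysis, ELISA timing is simply open; the lack of balance in controls remains either way.
- *That handling does vary by centre.* It may; the rule permits it and no more.
- *That centre differences can pass as a fingolimod effect in Visit 1 against Visit 2 or 3.* Constant offsets cancel there.

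Text is also blacked out directly after the -80°C rule in Protocol 6.5.1 and SAP section 4, the whole-blood sentence in 3.1 breaks off, and Figure 1 is not shown. Plate layout and run controls may be described there or in a laboratory manual, so their absence cannot be asserted. The control criteria, Table 6-2 and SAP 6.5 are readable, however, and contain neither balance nor adjustment.

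**Conclusion.** The point holds for controls against Visit 1, which is the primary comparison, and for controls against Visit 3. Nothing readable prevents controls from being concentrated by centre or date, and the planned tests do not adjust for either. The size is unknown. On the plan's IL-17 figures, an assumed net shift of 1.6 or 3.2 pg/ml takes the 5% error rate to about 9% or 21%; no imbalance means no bias from a fixed centre offset. For the within-patient contrasts, the concern is limited to storage age, plate allocation and flow drift, none of which can be quantified from the documents. This is an inexpensive improvement that should be made; it does not show that the results will be biased.

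A minor inconsistency goes with it: Protocol 6.5.1 sends serum for flow cytometry on the day of collection, while 3.1 refers to whole blood and 6.5.1 itself describes cells from venous blood.

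**What to change.** - **Protocol 3.1:** have each centre recruit controls roughly in proportion to its patients and over the same calendar period. The ratio is about one to one if 60 patients enter and three controls to four patients if 80 do (60/80), so the two figures need to be settled first. Record the site for controls as well as for patients.
- **Protocol 6.5.1:** put a patient's three serum samples on the same ELISA plate, spread controls over all plates, and record the dates of collection, transfer to -80°C and assay. Reconcile the serum wording for flow cytometry.
- **SAP 6.5.1 and 6.5.2:** stratify both control-versus-MS contrasts by centre, for example with a van Elteren test, or add a centre term where a t test would be used. State in advance how small centres are pooled, since each stratum needs both groups. As a sensitivity check, examine control levels against storage time (ELISA) and run date (flow cytometry).

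**Cost:** no extra patients, samples or assays. It takes some coordination of control recruitment and plate layout, and small strata may have to be pooled. Stratifying by centre does not correct storage age or flow drift; the plate rule and the drift check are there for those.

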### 3.2 Rationale of study design

This study design is not randomized or double blind, but it has no bias since the patients themselves will be their own controls if they fulfill the enrollment criteria.

This study was designed since there is accumulating evidence that Th1 and Th17-type immunities play major roles in multiple sclerosis pathogenesis in the last decade. By contrast, Th2 and Treg cytokines appear to counterbalance the production of Th1 and Th17 cytokines and thus play an ameliorating role in the natural course of multiple sclerosis. Not surprisingly, many multiple sclerosis medications exert their beneficial effects through modulation of these cytokines. The effects of fingolimod on cytokine production are largely unknown. So this study was designed to see to evaluate the effects of fingolimod on cytokine production.

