## **2 Study objectives**

### **2.1 Primary and key secondary objectives**

Primary objective of this study is:

-To evaluate the differences between serum cytokine and chemokine levels of healthy controls and multiple sclerosis patients

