**Table 6-2 Assessment schedule for Healthy Control Group**

Visit	1	2	3
Day	0	90±7	180±14
Obtain Informed Consent	X		
Evaluation of Inclusion/Exclusion Criteria	X		
Collecting Serum and Blood Samples	X		

Patients should be seen for all visits on the designated day with an allowed “visit window” of “7” days at visit 2 and “14” days at visit 3 , or as close to it as possible, or as shortly after it as possible, or as shortly before it as possible, etc.

At a minimum, patients will be contacted for safety evaluations during the 30 days following the last study visit or following the last administration of study treatment if there are post-treatment follow-up visits (whichever is later), including a final contact at the 30-day point. Documentation of attempts to contact the patient should be recorded in the source documentation.

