3 OBJECTIVES OF THE STUDY

3.1. PRIMARY OBJECTIVE

The primary objective of this study is to evaluate the differences between serum cytokine and chemokine levels of healthy controls and multiple sclerosis patients.

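### Protocol 3.2 says the design has no bias because patients are their own controls, but the primary contrast is between different people and the pre-post contrasts have no untreated MS series

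*Protocol*

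**What the plan says.** Protocol 3.2 (Rationale of study design) concedes that the study is neither randomized nor double blind, then says "it has no bias since the patients themselves will be their own controls". The synopsis repeats the sentence under purpose and rationale.

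The primary objective in Protocol 2.1 is "To evaluate the differences between serum cytokine and chemokine levels of healthy controls and multiple sclerosis patients"; SAP 3.1 states the same objective.

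Table 6-2 of the protocol, "Assessment schedule for Healthy Control Group", has visit columns for Days 0, 90 and 180, but the row "Collecting Serum and Blood Samples" is marked only at Day 0. For patients, Protocol 3.1 adds later sampling: "Additional serum and blood samples at 2 different time points will be collected from MS patients at months 3" and again at month 6. Protocol 3.4 says that a comparator arm does not apply, and 5.1.1 leaves the control group untreated.

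SAP 6.5.1 and 6.5.2 list four comparisons for each of 15 ELISA and 8 flow cytometry markers: Control vs Visit 1, Visit 1 vs Visit 2, Visit 1 vs Visit 3, and finally "Control group vs. Visit 3 (MS patients) by using appropriate statistical test". Control contrasts use the Mann-Whitney U or independent t test; within-patient contrasts use the Wilcoxon or paired t test.

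The synopsis and Protocol 1.2 say the three patient measurements will allow a test of whether fingolimod moves the cytokine balance and lowers inflammatory markers. Protocol 3.2 gives evaluating the drug's effects on cytokine production as the reason for the study.

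**The concern.** The no-bias sentence is the only justification the protocol gives for reading a change over six months as an effect of the drug. Self-control has no bearing on the primary contrast, because the two groups are different people. For the within-patient contrasts it removes only differences between people that stay constant over time. Anything else that changes between Day 0 and Day 180 remains mixed with the drug.

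At stake is what the report may conclude. If the sentence stands, a change in a marker between visits can be presented as a fingolimod effect on the authority of the protocol itself.

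**Working it through.** **1. The primary contrast.** Patients are aged 18-65 (Protocol 4.1). Controls must be over 18, with no upper limit and no matching rule. Protocol 9.8 sizes the study on matched pairs, but no section says how pairs are formed, and SAP 6.5 tests the groups as independent. The expected difference at Visit 1 is therefore

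Patient − Control = disease gap + differences in age, sex and other characteristics between the groups.

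Patients acting as their own controls removes nothing from the right-hand side.

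**2. The within-patient contrasts.** The mean of Visit 3 − Visit 1 is

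D = F + T + W + R + A,

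where F is fingolimod, T the time course without treatment, W continuing change after earlier therapy is stopped, R regression to the mean and A assay drift. The design observes D alone.

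- T: no untreated MS series exists (Protocol 3.4, Table 6-2).
- W: entry requires at least 1 month since steroids, interferon or glatiramer acetate, and at least 3 months since the other listed agents (Protocol 4.1). Levels may still be moving at Day 0.
- R: two of the three entry routes in Protocol 4.1 select on recent attacks or MRI activity. The third, intolerance of first-line treatment, does not. Selection is on disease activity, not on a cytokine, so regression in a cytokine is possible but depends on how closely the two are related. The documents do not give that.
- A: serum is frozen until assayed (Protocol 3.1) and levels are analysed together at the end (Protocol 6.5.1, SAP 6), so drift is limited for ELISA. Flow cytometry uses freshly isolated cells at each collection, so drift is mainly a concern there.

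Repeat samples from healthy controls would bear on A, but would not isolate W or R, which arise from being a selected and previously treated patient.

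**3. Control vs Visit 3.** Its expected value is the Visit 1 gap plus D. It measures distance from healthy levels at six months and does not isolate change.

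**4. An illustration, not an estimate of bias.** The documents give no figure for bias. The only effect size and SD are in Protocol 9.8: 7 and 15 pg/ml for IL-17. The stated 50 pairs reproduce if 15 is taken as the SD of the paired difference: (15 × 3.2415 / 7)² = 48.2, so 49 pairs by normal approximation; 50 pairs give 89.9% power by noncentral t (two-sided 0.05 assumed).

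Now assume a gap of 7 at both visits and no true change, SD 15 in both groups (the control SD is not given), 48-60 patients, 50-60 controls, and a visit correlation of 0.3-0.7 (not given). With t tests and 20,000 simulated trials per scenario:

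| Event, when nothing changes | Probability |
|---|---|
| Control vs Visit 3 significant | 64-72% |
| Significant at Visit 1, not at Visit 3 | 7-13% |
| The same, among markers significant at Visit 1 | 10-20% |
| Paired Visit 1 vs Visit 3 significant | about 5% |
| Significant at Visit 1, not at Visit 3, and paired test significant | about 1-1.7% |

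The third row depends heavily on the assumed gap: with 50-60 per group it is about 28-46% at a gap of 3.5, 2-6% at 10 and under 0.5% at 14.

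**The case against.** The strongest reply is that little in the analysis is wrong. Own controls is a fair description of Visit 1 vs Visit 2 and Visit 1 vs Visit 3, and the paired test of change is already in the same SAP sentence as Control vs Visit 3. Protocol 9.5 plans no special hypothesis. Some threats are mitigated: the last relapse must be at least 2 months before entry, steroids at least 1 month before, and samples during the study wait at least 1 month after a corticosteroid course (Protocol 5.4.6).

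Most of this stands. It limits the likely size of some terms in D but does not separate them from the drug, and it does nothing for the between-group primary contrast. It therefore cannot support a claim of no bias.

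A reader might infer that the SAP intends Control vs Visit 3 as a treatment effect, or as a test of normalisation. The documents do not say so; the SAP lists the comparison without a stated purpose. A reader might also take 10-20% as the share of this study's markers that would falsely look normalised. That is not supported: it takes one IL-17 difference, adds an assumed control SD and visit correlation, extends the result to markers with no stated gap, and applies only to someone who ignores the paired result. Replacing the Control vs Visit 3 test with a confidence interval would be a reporting preference, not a correction.

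**Conclusion.** The no-bias statement is wrong as written, in Protocol 3.2 and in the synopsis. This follows from the documents alone: different people in the primary contrast, one control sample on Day 0, and no untreated MS comparator. The within-patient contrasts are valid for change during treatment but do not identify a causal effect of fingolimod, so the purpose statements claim more than the design can deliver.

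The size and direction of any bias cannot be derived from the documents. The simulated figures are illustrative and show only that significance against controls at one visit and not at another is poor evidence of change. The point does not make the 50 pairs arithmetically wrong, and it is no reason to drop the Control vs Visit 3 test. What it alters is the conclusion the trial may draw.

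**What to change.** 1. Delete the no-bias statement from Protocol 3.2 and the synopsis.
2. State in both documents that Visit 1 vs Visit 2 and Visit 1 vs Visit 3 estimate change during treatment in an uncontrolled pre-post comparison, not a causal effect of fingolimod.
3. Reword the synopsis and Protocol 1.2, where they say the study can test whether fingolimod shifts the cytokine balance, to match.
4. In SAP 6.5, base any statement about change on the within-patient contrasts already planned.
5. In the same place, say that Control vs Visit 3 describes distance from healthy levels, and that significance at Visit 1 followed by non-significance at Visit 3 is not evidence of normalisation. The test may remain.

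The cost is a wording amendment to the protocol and SAP. No visits, samples, patients or analyses are added or removed; the conclusion becomes more modest.
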